## **5.6 Anticipated Adverse Events**

There are risks associated with endovascular embolization with or without stent-assist coiling procedure to treat cerebral aneurysms. These standard risks may include the following:

- Adverse reaction to antiplatelet/anticoagulation agents or contrast media
- Air embolus
- Allergic reaction/toxic effects
- Bleeding
- Death
- Device migration or misplacement
- Device Fracture
- Dissection of the parent artery
- Embolism
- Fever
- Foreign material embolic event
- Groin injury

- Headache
- Hemolysis
- Hemorrhage
- Hydrocephalus
- Infection
- Intracerebral bleeding
- Ischemia
- Neurological deficits
- Occlusion of unintended vessel
- Parent Artery Stenosis
- Perforator occlusion
- Peripheral embolism
- Post-procedure bleeding
- Ruptured or perforated aneurysm
- Recanalization
- Residual flow
- Seizure
- Stroke/TIA
- Surgical intervention
- Thromboembolism
- Vascular access site complication
- Vasospasm
- Vessel perforation
- Vessel trauma/perforation/occlusion
- Vision impairment

## 5.7 Subject Death

Subject death during the investigation must be reported via eCRF within 24-hours of Investigator's knowledge of the death. Notification of death must include a brief statement of the relevant details of the death and is required to be signed by the Investigator. In addition, all patient deaths must be reported to the specific Ethics Committee and Competent Authority in accordance with regulatory requirements. The method of declaration will conform to the current regulations. A copy of the death records, death certificates and an autopsy report (if performed) are required to be sent to Corindus or designee, within ten (10) days following the death.

In the event of subject death, efforts should be made to perform an autopsy in order to assess the state of the heart. For subjects that do not undergo autopsy, written documentation from the Investigator will be required providing justification as to why an autopsy was not performed.

## 5.8 Surveillance Committee

A Surveillance Committee will be composed of three expert physicians in the field of interventional neuroradiology and/or neurosurgery, who are independent and not directly involved in the conduct of the trial. The purpose of the committee is to review and adjudicate all complications/adverse events as they occur over the course of the study (classify, identify causal relationship between event and device, procedure or subject). The committee will also review and adjudicate, as necessary, issues relating to classification of events as major (serious) or minor (non-serious), and attribution to system, treatment and/or disease. The neurological outcomes and adverse events will be reported under the clinical investigation and any imaging generated will be forwarded to the committee. The committee will analyze the relationship between the images and the cause of the neurological deterioration. Any overall trends or conclusions drawn from these analyses will be reported; however, no specific criteria will be applied.

## 6. STATISTICAL CONSIDERATIONS AND ANALYSIS

Data for subjects that undergo an endovascular procedure where the Corindus GRX device is used (or attempted to be used) will be included in both primary and secondary endpoints where data are available.

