#### 3.3 Primary Safety Endpoint

The primary safety endpoint will be a composite of intra- and peri-procedural events, defined as vascular injury including intraprocedural aneurysm rupture caused by robotically controlled catheters, wires, or devices and thromboembolic events with neurological decline (NIHSS score change  $\geq 4$ ) within 24-hours post-procedure or hospital discharge, whichever occurs first.

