##### Post-CorPath Procedure Subject Evaluations

- NIH Stroke Scale (NIHSS) and Modified Rankin Scale (mRS) conducted by a trained person with appropriate qualifications to perform these evaluations are required to be performed within 24-hours post procedure or prior to discharge, whichever occurs first.
- Raymond Grade-Roy Occlusion Classification Scale conducted by a trained person with appropriate qualifications to perform this evaluation:
  - Class (I): Complete occlusion – complete obliteration of the aneurysm
  - Class (II): Residual neck – persistence of any portion of the original defect of the arterial wall as seen on any single projection, but without opacification of the aneurysmal sac.
  - Class (III): Residual aneurysm – opacification of the aneurysmal sac.
    - Class IIIa: contrast opacification within the coil mesh
    - Class IIIb: contrast opacification outside coil mesh
- Additional post procedure clinical assessment (scales/scores) is left to the discretion of the investigator and shall be dictated by the patient's clinical symptoms
- Record of all Adverse Events (AEs)
- If clinically indicated by the Investigator and/or if performed under standard hospital procedure, record lab values closest to 24-hours post-procedure or discharge:
  - Hemoglobin (HGB)
  - Hematocrit (HCT)
  - Activated Partial Thromboplastin Time (aPTT)
  - Platelet count
  - International Normalized Ratio (INR)
  - Serum Creatinine
  - Glomerular Filtration Rate (GFR)

- Before the subject is discharged from the hospital, it is recommended that telephone numbers and contact information be confirmed with the subject (and/or authorized legal guardian) to ensure the ability to contact him/her after discharge from the hospital for scheduling of the 90-day ( $\pm$  14 days) telephone evaluation.

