## 6.9 Handling of Missing Data

It is assumed that because the primary and most secondary analyses are evaluated within 24-hours of CorPath GRX procedure or prior to hospital discharge, whichever occurs first, there will be minimal missing data. For the 90-day and 180-day secondary endpoints (modified Rankin Scale, thromboembolic events, and aneurysm occlusion), all practical monitoring and follow-up steps will be taken to ensure complete and accurate data collection. Additionally, all data collected on safety or adverse events will be reported to the extent they are available.

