4.1 Definition of Analysis Populations

Analysis Cohort: Any subject with an attempted endovascular procedure (a non-missing robotic microcatheter insertion time).

Per-Protocol Cohort: Any subject in the analysis cohort who did not have a major protocol deviation.

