4.3 Primary Safety Endpoint

Objective: To assess safety of using CorPath GRX for robotic-assisted endovascular procedure.

Hypothesis:

$H_0: p \geq 15\% (5\% + 10\% \text{ NI margin})$

$H_a: p < 15\%,$

where p =proportion of patients with a safety event.

Endpoint: The proportion of subjects with a safety event where a safety event is intra- and peri-procedural events, including target aneurysmal rupture, vessel perforation or dissection, and thromboembolic event with neurological decline within 24 hours post-procedure or hospital discharge, whichever occurs first.

Subjects to Include: Analysis Cohort

Statistical Analysis: The proportion of subjects with a safety event as defined will be summarized along with a 2-sided Clopper Pearson Exact 95% confidence interval. If the upper bound is less than 15%, we will declare success and conclude that safety is not worse than the performance goal of 15%.

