4.5 Additional Summaries

Some additional summaries will be prepared:

- Descriptive statistics of the population
 - Demographics and patient baseline characteristics

- Aneurysm characteristics
- Procedures performed
- Malfunctions
- Protocol deviations

5 Data Conventions and Missing Data

It is assumed that because the primary and most secondary analyses are evaluated within twenty-four (24) hours of CorPath GRX procedure or prior to hospital discharge, whichever occurs first, there will be no missing data. For the 90-day and 180-day secondary endpoints (modified Rankin Scale, thromboembolic events, and aneurysm occlusion), all practical monitoring and follow-up steps will be taken to ensure complete and accurate data collection. Additionally, all data collected on safety or adverse events will be reported to the extent they are available.

6 Appendix 1: Adverse Event Classification and Definitions

An Adverse Event (AE) is any untoward medical occurrence, unintended disease or injury, or untoward clinical signs (including abnormal laboratory findings) in subjects, users or other persons, whether or not related to the investigational medical device.

A Serious Adverse Event (SAE), as per the European Standard ISO 14155 (E), is an AE that:

- Led to death
- Led to a serious deterioration in the health of a patient that:
- Resulted in a life-threatening illness or injury
- Resulted in a permanent impairment of a body function or body structure
- Required in-patient hospitalization or prolonged hospitalization
- Resulted in medical or surgical intervention to prevent permanent impairment to a body function or body structure
- Led to fetal distress, fetal death or a congenital abnormality or birth defect.

In the current study indication, a SAE can be defined as an adverse event where the outcome is one of the following:

- Incidence of death 24 hours post procedure
- Target aneurysm rupture
- Vessel perforation
- Vessel dissection
- Thromboembolic complication
- Failure to navigate to target
- Device failure to respond to input, or other intra-operative device failure

Adverse Event Assessments

Relatedness:

- Procedure-related: Event has a strong temporal relationship to the study procedure. This includes AEs attributable to any device(s) used at procedure, such as access devices, delivery microcatheters, embolic coils, non-ionic contrast, guidewires, or any other adjunctive, approved/cleared device for treatment of intracranial aneurysms.

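### Neither document says how a thromboembolic event without a post-procedure NIHSS is classified for primary safety, and both primary denominators depend on which data exist

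*Protocol*

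**What the plan says.** Protocol section 6 opens with the inclusion rule: subjects in whom the device was used, or its use attempted, "will be included in both primary and secondary endpoints where data are available". This is an available-case rule, and it names the primary endpoints.

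On missing data, Protocol 6.9 expects that "there will be minimal missing data". SAP section 5 goes further: "there will be no missing data". Both rest on the short observation window. Neither gives a denominator rule, an imputation rule or a sensitivity analysis for the primary endpoints.

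SAP 4.2 and 4.3 analyse both primary endpoints in the Analysis Cohort, which SAP 4.1 defines as "Any subject with an attempted endovascular procedure (a non-missing robotic microcatheter insertion time"). A missing field therefore helps set the denominator.

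Protocol 3.3 lists among the safety events "thromboembolic events with neurological decline" and defines decline as an NIHSS change of at least 4. Protocol 6.2 says major stroke instead, which Protocol section 13 also defines by an NIHSS increase of at least 4. SAP 4.3 has "thromboembolic event with neurological decline within 24 hours post-procedure or hospital discharge, whichever occurs first", with no threshold.

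Collection is compulsory: under the Post-CorPath Procedure Subject Evaluations in Protocol 4.8.9, the NIHSS and mRS "are required to be performed within 24-hours post procedure or prior to discharge, whichever occurs first". Protocol 5.8 and 9.2 provide for adjudication. No passage says how to adjudicate when the score is absent.

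**The concern.** One component of the primary safety composite cannot be determined without a post-procedure NIHSS. If a subject has a thromboembolic event and the score is not obtained, the documents leave two routes. Under Protocol section 6 the subject has no data for the endpoint and leaves the denominator. Under the SAP the subject stays in the cohort, but the event does not meet its definition and is not counted. Either route lowers the observed safety rate.

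The reason for a missing score may be related to harm, for example a subject who remains sedated, has returned to the angiography suite, or has died. Death is not itself a listed component of the composite. The trial has a single arm, so no control group shares the bias, and without a rule the choice would be made with the data in view.

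**Working it through.** **Inputs.** Protocol 6.6 and SAP 3.2: safety 5% expected against a goal of 15%, N = 96 for at least 90% power; effectiveness 90% expected against 80%, N = 108 for at least 80% power; overall N at least 108. SAP 4.2 and 4.3: two-sided 95% Clopper-Pearson interval, which corresponds to one-sided 0.025. The rate of missing NIHSS is not in the documents; any rate used below is an assumption.

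**1. The plan's own figures.** n = [(z₁₋α√(p₀(1−p₀)) + z_power√(p₁(1−p₁))) / |p₁−p₀|]², with one-sided α = 0.025.

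- Safety: [(1.960 × 0.3571 + 1.2816 × 0.2179) / 0.10]² = 95.87, so 96.
- Effectiveness: [(1.960 × 0.40 + 0.8416 × 0.30) / 0.10]² = 107.43, so 108.

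Both reproduce.

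**2. The safety boundary at n = 108.** Upper Clopper-Pearson limit for x events: the 0.975 quantile of Beta(x+1, n−x).

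- 8/108: 14.07%, pass.
- 9/108: 15.23%, fail.

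At most 8 events are allowed.

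**3. One or two unscored thromboembolic events, with 8 other events already counted.**

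| Unscored | Dropped | Kept as event-free | Counted as event |
|---|---|---|---|
| 1 | 8/107: 14.20%, pass | 8/108: 14.07%, pass | 9/108: 15.23%, fail |
| 2 | 8/106: 14.33%, pass | 8/108: 14.07%, pass | 10/108: 16.37%, fail |

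At this boundary the convention decides the result.

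**4. Near the planned rate.** 5% of 108 is 5.4, so about 5 events. With 5 counted events (5/108: 10.47%), three unscored subjects counted as events give 8/108 and still pass. A fourth gives 9/108 and fails, whereas dropping those four gives 5/104 (10.86%) and passes.

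**5. Error rate.** At a true rate of 15%, the exact chance of passing is P(X ≤ 8 | 108, 0.15) = 0.0134. If one true event goes uncounted while the subject stays in the denominator, it becomes P(X ≤ 9) = 0.0289, above 0.025. With two uncounted it is P(X ≤ 10) = 0.0559.

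**6. Effectiveness.** The NIHSS plays no part. The exposure is the protocol's availability clause and the SAP's insertion-time condition. Lower limits: 95/108 gives 80.3% and passes; 94/108 gives 79.2% and fails; 94/107 gives 80.1% and passes. Excluding one subject who was not a success can reverse the conclusion.

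**7. Why a blanket penalty should not be the primary rule.** Suppose every missing score counted as an event, at an assumed missing rate r. With a true rate of 5%, the counted rate is 0.05 + 0.95r, and power P(X ≤ 8 | 108) is 0.908 at r = 0, 0.806 at 1%, 0.671 at 2% and 0.523 at 3%. That is a heavy price if most unscored subjects had no thromboembolic event.

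**The case against.** The strongest reply is that the protocol already guards against this. The NIHSS is mandatory for every subject, Protocol 8.1 promises full source verification, an independent committee reviews adverse events and imaging, and endpoint events get site-independent review from narratives and source data. Few scores should be missing. This stands and limits the size of the problem. But a requirement to collect a score does not say what happens without one, and Protocol 8.3 itself gives uncompleted required testing as an example of a deviation.

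Three stronger readings are tempting and are not supported.

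- *That the plan says an unscored subject is dropped or counted as event-free.* It says neither; both follow from the absence of a rule. The SAP cohort is not defined by NIHSS availability, so under the SAP such a subject stays in the denominator.
- *That missing NIHSS undermines both primary endpoints, or the whole safety composite.* Rupture, perforation and dissection count without a score, and effectiveness does not use it. The exposed subject has a thromboembolic event, no vascular injury and no score.
- *That the safety test will in practice turn on one event.* That is so only at the boundary. At a true 5%, exactly 8 events in 108 has probability of about 8%. If all 120 permitted subjects were analysed, 10 events would still pass (10/120: 14.79%).

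Nor do the documents say that a sedated or ventilated subject cannot be scored. That missingness may relate to harm is a reasonable inference, not a stated fact.

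**Conclusion.** The concern holds in a limited form. The rule for a thromboembolic event without a post-procedure NIHSS is missing, the two readings the documents allow both favour the device, and the protocol and SAP differ on who is in the denominator. The SAP's insertion-time condition is the one place where a missing field is written into both primary denominators.

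The likely effect is small. It can change the safety conclusion only when the count is near 8 of 108, or when four or more unscored events are added to about 5. This assumes 108 analysed subjects and the stated exact interval; the number of missing scores is unknown and should be low. It should be corrected because a fixed rule is cheap and removes a choice that would otherwise be made after the data are seen.

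**What to change.** Amend Protocol section 6 and SAP 4.1, 4.2, 4.3 and 5 as follows.

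- Define both primary denominators as all subjects in whom CorPath use was attempted, whether or not any field, including the insertion time, is missing.
- Remove the availability clause for the primary endpoints, and remove the SAP's statement that no data will be missing.
- Count an adjudicated thromboembolic event without a valid post-procedure NIHSS as a safety event, unless the Surveillance Committee documents from source a decline below 4 points.
- Count a missing effectiveness outcome as failure.
- Pre-specify a worst-case and tipping-point table, as a sensitivity analysis only, in which other treated subjects without an NIHSS count as safety events.

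The cost is a few sentences and one table. Reported rates may be slightly less favourable. If the data are complete, as the sponsor expects, the result is unchanged. Keeping the blanket penalty out of the primary analysis avoids the loss of power shown in step 7.

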### 6.1 Analysis of Primary Effectiveness Endpoint

The primary effectiveness endpoint will be defined as successful completion of the robotic-assisted endovascular procedure absent any unplanned conversion to manual operation for guidewire, microcatheter, embolization coil(s), intracranial stent(s), or inability to navigate vessel anatomy. The proportion of subjects with a successfully completed endovascular procedure will be summarized along with a 2-sided 95% exact binomial confidence interval to demonstrate that the effectiveness is not inferior to a performance goal based upon historical rates from recent literature for comparable procedures.

### 6.2 Analysis of Primary Safety Endpoint

The primary safety endpoint will be a composite of intra- and peri-procedural events, including target aneurysmal rupture, vessel perforation or dissection, and major stroke within 24-hours of post-procedure or discharge, whichever occurs first. The proportion of subjects with a safety event as defined will be summarized along with a 2-sided 95% exact binomial confidence interval to demonstrate that safety not inferior to a performance goal based upon historical rates from the literature for comparable procedures.

### 6.3 Analysis of Secondary Endpoints

Secondary endpoints will be analyzed with descriptive statistics along with a 95% confidence interval. Descriptive statistics for categorical variables will include the number and percentage of subjects in each category, with two-sided 95% confidence intervals of the percentage of subjects in each category. Descriptive statistics of continuous variables will include sample size, mean standard deviation, minimum, median, maximum, and 95% confidence interval of the mean. Summaries will be provided for the overall population and by type of aneurysm (ruptured or unruptured).

#### 6.4 Determination of Historical Controls

Safety rates from key literature are presented in Table 2 below:

**Table 2. Rates of safety from literature for endovascular treatment of unruptured and ruptured aneurysms.**

	N Aneu- rysms (Pts)	Mortality at Discharge	Overall Complication Rate	Rupture/ perforation Rate (%)	Embolism Rate (%)
UNRUPTURED INTRACRANIAL ANEURYSMS					
Algra et al 2018*	73066 (71819)	0.3% (0.2% - 0.4%)	4.96% (4.00, 6.12%)	0.9% (212/18520) 95% CI (0.6%, 1.3%)	2.82% (437/16000) 95% CI (2.3, 3.5%)
Advanced Endovascular Methods**	2248	0.4% (0.2 - 1.1%)	6.1% (4.3, 8.7%)		
Kawabata et al 2017	1406 (1375)			1.4% (20/1406)	
coil only	340			1.8% (6/340)	
stent-assisted coiling	468			0.9% (4/468)	
balloon-assisted coiling	598			1.7% (10/598)	
From Lit Review, Table 6 in Kawabata	7785	0		1.4% (108/7785)	
Zheng et al 2016	1127			1% (11/1127)	
Santillan et al 2013	217	0%		5% (3/217)	
Shigematsu et al 2013	4767			1.4% (65/4767)	
Oishi et al 2012	500	0%		1.4% (7/500)	
Im et al 2009	435	0%		0.9% (4/435)	
Pierot et al 2008	739	0.3%		2.4% (18/739)	
Pierot et al 2008 (ATENA study)	739 (649)  (700 procs)	1 month 1.4%	15.4%	2.4% (18/739)  2.6% (18/700)	7.3% (29/308)  7.1% (per proc)

	N Aneurys ms (Pts)	Mortality at Discharge	Overall Complication Rate	Rupture/ perforation Rate (%)	Embolism Rate (%)
Pierot et al 2009, (ATENA study, coil alone results)	325 pts	0.9% (3/325)	10.8% (35/325)	2.1% (7/325)	6.2% (20/325)
RUPTURED INTRACRANIAL ANEURYSMS					
Zhang et al 2019	1004	All cause 9.5% (5.8%, 13.2%) proc related 1.8% (0.9, 2.7%)	22.7%*** 95% CI (15.1, 30.3%)		
Cognard et al 2011 (CLARITY GDC study)	405	1.50%		3.7% (15/405)	13.3% (54/405)
Pierot et al 2011 (CLARITY)	608	5.1% (31/608) cum. TRT related morb/mort rate  19.6% (119/608) cum. morb/mort rate)	17.4% (106/608)	4.6 (28/608)	

\* rates presented are pooled crude risk from meta-analysis modeling

\*\* Advanced = Stent-assisted coiling, balloon-assisted coiling, flow diverting stents or woven endo-bridge devices.

\*\*\* definition not specified

Additionally, there were three randomized controlled trials comparing different endovascular treatments that contained both ruptured and unruptured intracranial aneurysms: HELPS, MAPS, and Cerecyte Coil trial. Rates presented pooled results from both arms in the following three tables.

**Table 3a-3c. Rates presented pooled results from both arms from three (3) from randomized control trials.**

HELP Trial	N	Mortality	Procedural aneurysm rupture*	Thromboembolic complication*		
White et al 2008  N=499 RCT, covered vs uncovered coil  53% ruptured	499	2.2% (11/499) At discharge	3.4% (17/499)	9.8% (39/499)		

\* Article specifically called out that “some of these adverse events, especially procedural ones, did not result in permanent clinical sequelae.

MAPS Study	N	Mortality	Overall Complication Rate	Clinical Event Committee Adjudicated			Technical Success
				Rupture/re-rupture	Ischemic Stroke	Hemorrhagic Stroke*	
McDougall et al 2014  N=626 RCT, Matrix coil vs GDC coil  Ruptured 36.4% (228/626)	626	0.2% (1/626) Peri-proc  2.4% (15/626) 30 day	14.9% (93/626)	0.3% (2/626)	3.4% (21/626)	1.1% (7/626)	97.1% (608/626)

\*Article notes hemorrhagic strokes due to rupture/re-rupture are not included in Hemorrhagic Stroke summary

CERECYTE Coil Trial	N	Mortality	Overall Complication Rate	Rupture/re-rupture	Thromboembolic complication	Neuro-deterioration	Technical Success
Coley et al 2012  N=500 RCT, Cerecyte vs bare platinum coil  Ruptured 46.9% (233/500)	497	0% within 24-hr  0.4% (2/497) before discharge	12.3% (61/497)	3.6% (18/497)	5.6% (28/497)	3.0% (15/497)	97.2% (483/497)  (14 “unable to place coil”)

While Cerecyte and HELPS present overall complication rates in the 12-15% range, it was felt that the rates of stroke, rupture/re-rupture and death from the MAPS trial that were adjudicated by an independent clinical event committee were the most accurate to represent the expected rates of safety events for this trial. If we assume independence and add the individual rates, the

expected rate of safety events is 4.8% (30/626) but will be rounded to the nearest percent of 5% for sample size calculations.

The performance endpoint is similar to a technical success measure. Zang *et al* 2019 provided a literature review that included technical success. The weighted average was 97.6% for ruptured aneurysms. McDougall *et al* 2014 reported a similar overall procedural success of 97.1% (608/626) and Coley *et al* 2012 report a success of 92.7%, but this number does not include conversion to manual as our performance endpoint does.

For the conversion to manual aspect, there are not data available for treatment of intracranial aneurysms, but we can look at past Corindus CorPath performance for PCI. In Table 4 below, the premarket trial results 1.2% for unplanned conversions, but the rate was considerably higher in the real-world post-market trial with 10.4% unplanned conversions.

To estimate the overall rate of success for the performance endpoint, we will use the highest rate of 10.4% rounded to the nearest percent of 10%, or in terms of success, 90% expected performance success rate.

